
Methods:

This is a randomized controlled open-label trial comparing two groups of women with preterm labor who are treated with either indomethacin or nifedipine as a tocolytic agent. The study will be conducted at each of the five University of California medical center hospitals. In order to be admitted to the hospital for tocolytic treatment, subjects will have to be in preterm labor defined as regular uterine contractions (at least 6 per hour) associated with changes in cervical dilatation and/or effacement, cervical dilatation of > 2 cm at presentation or a change in cervical dilatation of > 1 cm, and > 25 to 50% effacement and/or a short cervical length (per institution's policy) as obtained by transvaginal cervical sonography with or without a positive fetal fibronectin. All women will be treated in a uniform fashion with initial hydration, evaluation for etiologic infection, administration of antenatal corticosteroids to accelerate fetal maturity, and magnesium sulfate for neuroprotection. Magnesium will be administered according to each institution's magnesium for neuroprotection protocol. Women will be randomized to either tocolytic therapy with nifedipine or indomethacin by using computerized randomized block sequencing.

Nifedipine Treatment: Subjects will be given nifedipine 10mg orally and repeated every 20 minutes for a maximum dose of 30mg in the first hour followed by 20mg every 6 hours for the first 48 hours of treatment. This is a commonly used dose and has been described in a large meta-analysis reviewing nifedipine in the management of preterm labor by Conde-Agudelo et al.¹ Of the 26 studies reporting on nifedipine as an acute tocolytic, the dosing ranged from a loading dose of 10 to 30mg orally or sublingually, followed by 10 to 20mg orally every 4-8 hours. 12 of those studies used a repeat loading dose every 15-20 minutes. The decision was made to proceed with nifedipine 10mg orally and repeated every 20 minutes for a maximum dose of 30mg followed by 20mg every 6 hours since it is a commonly prescribed dosing for acute tocolysis.

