
Statistical Analysis:

The purpose of this study is to determine whether nifedipine or indomethacin is superior in arresting preterm delivery by 48 hours. We expect the nifedipine group to arrest preterm labor for 48 hours in 72% of cases¹ and the indomethacin group to arrest preterm labor for 48 hours 83% of cases.² Using a power of 80%, alpha of 0.05 we calculate 225 subjects are needed in each group.

The primary outcomes and other dichotomous outcomes will be evaluated using Chi-square. We also anticipate a 25% difference between groups based on prolongation of pregnancy by one week based on a small RCT using nifedipine vs. ritodrine conducted by Papatsonis et al.³ Continuous variables will be compared using Student's t-test. Sub-group analyses will be done to compare differences across the sites. Regression analyses will be applied where appropriate such as for neonatal complications and the consideration of gestational age.

3. Papatsonis et al. Nifedipine and ritodrine in the management of preterm labor: a randomized multicenter trial. *Obstet Gynecol* 1997; 90:230-4.

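### Block randomisation in an open-label five-site trial is stated without site stratification, protected block lengths or allocation concealment, and the primary test has no site term

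*Combined protocol and SAP*

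**What the plan says.** The Methods section covers sequence generation in one sentence: women are "randomized to either tocolytic therapy with nifedipine or indomethacin by using computerized randomized block sequencing". The same section gives the setting: "This is a randomized controlled open-label trial comparing two groups of women with preterm labor", and "The study will be conducted at each of the five University of California medical center hospitals".

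Several things are left to local policy:
- Entry: one route into the definition of preterm labor is "a short cervical length (per institution's policy) as obtained by transvaginal cervical sonography".
- Co-treatment: "Magnesium will be administered according to each institution" and its own neuroprotection protocol. Methods also leaves use of magnesium alongside the study drug to local providers, and counts starting magnesium as tocolytic failure.
- Stopping: under Summary, whether study drug stops when magnesium starts depends on the institution.

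The Statistical Analysis section assigns a chi-square test to the primary outcome and mentions no adjustment for site. Site appears once: "Sub-group analyses will be done to compare differences across the sites".

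The document does not say whether there is one list or five, how long the blocks are, whether their length varies or is withheld from sites, or how an assignment is concealed until a woman is enrolled.

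**The concern.** Staff in an open-label trial see every assignment. If each site has its own list in short fixed blocks, the team recruiting the next woman can work out the end of each block. Entry leaves room for judgement, because the definition of preterm labor joins several criteria with and/or and one is set locally. Someone who foresees the next drug could therefore, knowingly or not, approach women nearer to or further from delivery. That is a systematic bias in the 48-hour comparison. A chi-square test cannot detect it, and it cannot be repaired after enrolment.

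If all sites share one list, foreseeing is harder, since each site sees only its own part of the sequence. But nothing then balances the arms within a site, although site practice may well affect outcome and the primary test ignores site.

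**Working it through.** Inputs from the plan: 72% and 83% pregnant at 48 hours, 225 per group (450 in total), power 80%, alpha 0.05, five sites. The plan gives no block lengths, site sizes or site-level rates; those below are assumptions.

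1. **The plan's own figure.** Two-sided, pooled variance, no continuity correction: n = [1.96·√(2·0.775·0.225) + 0.8416·√(0.72·0.28 + 0.83·0.17)]² / 0.11² = 225.04, or 226 rounded up. Power at 225 is 79.99%. The 225 reproduces, and nothing here changes it.

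2. **Predictability, one list per site, fixed block of length 2k.** The share of assignments known with certainty is 1/(k+1). Guessing the arm with more places left is right k + 4^k / (2·C(2k,k)) − ½ times per block.
   - Block 4: certain 1/3 = 33%; correct 2 + 16/12 − 0.5 = 2.83 of 4 = 71%.
   - Block 6: certain 1/4 = 25%; correct 3 + 64/40 − 0.5 = 4.10 of 6 = 68%.
   - Block 8: certain 1/5 = 20%; correct 4 + 256/140 − 0.5 = 5.33 of 8 = 67%.

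   Chance alone gives 50%. Certainty requires knowing the block length. The guess needs only a complete record of that site's assignments, because the arm with more places left is the arm that is behind.

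3. **What guessing could do (illustration).** Suppose recruiters enrol women whose 48-hour success chance is 5 points better or worse according to the guessed arm. With blocks of 4, the false difference is 2·5·(2·0.708 − 1) = 4.2 points, against the planned 11. The standard error at a base rate of 77.5% is √(2·0.775·0.225/225) = 3.94 points, so the shift is 4.17/3.94 = 1.06 standard errors. Two-sided type I error rises from 5% to about 18%. With a 3-point selection the figures are 2·3·0.417 = 2.5 points and about 10%.

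4. **Imbalance, one shared list.** Simulation: 450 women allocated to sites at random, one trial-wide blocked list (blocks of 4, of 6, or a mix of 4, 6 and 8), 3,000 runs each.
   - Equal sites (about 90 women each): the median within-site difference between arms is 6 women and the 95th percentile is 16-17. At least one site is 60:40 or worse in 16-17% of trials.
   - Shares of 40/25/15/12/8% (smallest site 0.08·450 = 36 women): 38-39%.

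5. **Effect of that imbalance on the overall result.** Let site success rates lie at −10, −5, 0, +5 and +10 points around the mean. With equal sites their standard deviation is √[(100+25+0+25+100)/5] = 7.07 points. The shift in the arm difference has standard error 7.07·√(2/225) = 0.67, so 95% of trials lie within 1.96·0.67 = 1.3 points. The simulation agrees: 1.3 for equal sites and 1.2 for the unequal shares.

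**The case against.** The strongest reply is that silence is not a defect. The stated phrase also fits per-site lists with randomly varying, undisclosed blocks, which would largely avoid both weaknesses. That stands. A reader might infer that the trial does use fixed blocks with no stratification and no concealment; the documents do not say so. They state no safeguard either, so the point is what the text permits and what better scheme should replace it.

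The predictability figures are conditional. They need per-site lists and someone tracking every assignment, and the certain share also needs a fixed, known length. Open-label status alone does not reveal the next assignment. This stands too, and the 20-33% and 67-71% are the size of the exposure, not an estimate of what will happen.

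The two harms are alternatives and must not be added: within-site imbalance belongs to a shared list, foreseeability mainly to per-site lists.

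A reader might also infer that an uneven split within a site confounds drug with local practice in the planned site comparisons. It does not. All women at a site are under the same local policy, so a 60:40 split there costs only precision. Confounding by site could enter only the pooled comparison, where step 5 shows it is small.

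**Conclusion.** The concern holds as a weakness in the stated design. One sentence on blocks, in an open-label trial at five sites with differing policies, leaves room for foreseeable assignments or for arms unbalanced within sites, and the primary test makes no use of site.

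Predictability is the main risk, because selection on a foreseen assignment is systematic. The false difference of 2.5 to 4.2 points in step 3 rests on assumed selection of 3 to 5 points and blocks of 4. Chance imbalance by site is secondary: about 17% to 39% for at least one site at 60:40 or worse under the assumed site sizes, but about 1.3 points or less on the overall difference in 95% of trials.

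The point should be addressed. It does not show that the trial's comparison is biased, and it leaves the sample size unchanged.

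**What to change.** State in Methods that the computer-generated sequence is stratified by site, with randomly varying block sizes that are not disclosed to sites, and that each assignment is released only after eligibility and consent are recorded. Keep the block sizes out of any document the sites hold. In Statistical Analysis, replace the pooled chi-square for the primary outcome with a site-stratified test, for example Cochran-Mantel-Haenszel.

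The parts belong together. Stratifying by site makes guessing easier than under one shared list, so it should not be adopted without the undisclosed varying lengths. Those remove nearly all certain assignments but not every guess: with blocks of 4, 6 and 8 equally likely, someone tracking a site's assignments would still be right (2.83 + 4.10 + 5.33)/18 = 68% of the time.

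Cost: a change to the randomisation program, a protocol sentence and an analysis-plan line, with no extra patients. The downside is a short step before the first dose in an acute setting. Methods describes the online database as holding uploaded case report forms and supporting analysis and communication; it does not say whether it can release assignments. That must be confirmed, or another central route arranged. If the sponsor already works this way, writing it down costs almost nothing.

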2. Other secondary maternal outcomes included will be maternal adverse side effects significant enough to stop or delay medication use, need for a second tocolytic to halt preterm contractions. Neonatal outcomes measured will be respiratory distress syndrome (RDS), interventricular hemorrhage (IVH), patent ductus arteriosus (PDA), necrotizing enterocolitis (NEC), intubation, number of NICU days and neonatal mortality.

Existing Knowledge:

Specifically we intend to answer the question of which of these two tocolytics should be used as a first line agent. Again there is much evidence showing that calcium channel blockers and prostaglandin inhibitors are the two classes of medications that are superior in delaying delivery for up to 48 hours, decrease RDS, neonatal mortality and maternal side effects compared to other medications.² There has been one poorly designed small study directly comparing nifedipine to indomethacin.³ Another study compared magnesium to nifedipine and to indomethacin. Again, this study had an inadequate sample size. In addition, there was crossover of tocolytic groups, which does not allow for direct comparison. Women in preterm labor typically present with painful contractions and some degree of cervical dilation. There is a small window to treat these patients in an attempt to arrest preterm labor. Using the optimal tocolytic agent initially can potentially prevent or delay preterm birth with its resultant neonatal morbidity and mortality.

Previous Research:

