Indomethacin Treatment: Those randomized to indomethacin will be given 100mg orally as a loading dose followed by 50mg every 6 hours for the first 48 hours of treatment. This regimen was decided after reviewing the Cochrane review on COX inhibitors for treating preterm labor.² 10 of the 13 trials included in the review used indomethacin. The dosing ranged from 50 to 100mg loading dose followed by 25mg to 50mg orally every 4-6 hours. The loading dose was mostly given rectally. A recent randomized control trial compared indomethacin vs. two other tocolytics.³ The indomethacin dosing used was an initial 100mg suppository, repeated one time if contractions persisted after two hours, followed by 50mg orally every 6 hours. This regimen was associated with increased incidence of fetal ductal constriction (13/97) and oligohydramnios (5/97) when compared to the other two treatment groups. Therefore, we propose using a one time loading dose of 100mg orally followed by 50mg every 6 hours, which is a commonly prescribed dosing. Using the lower end of the normally prescribed dosing range should have decrease fetal and maternal side effects.

Tocolytic failure will be defined as delivery within 48 hours of initiation or the start of magnesium for neuroprotection. Magnesium for neuroprotection is started when delivery is deemed imminent, so when initiated, it is implied that there has been tocolytic treatment failure. That being said, it is difficult to predict preterm birth, especially in the setting of preterm labor, and some clinicians may start magnesium for neuroprotection without labor proceeding to delivery. There is a theoretical risk of neuromuscular blockade with the concurrent use of magnesium and nifedipine, and there have been 2 case reports of reversible neuromuscular blockade in this setting.^{4,5} One of these case reports used a total dose of 500mg of magnesium⁵ – which is significantly more than what would be administered for our neuroprotective dosing. There are studies, albeit small, that show concurrent use of nifedipine and magnesium is safe in the setting of preeclampsia.^{6,7,8} One such study describes expected hemodynamic changes with the concurrent use of nifedipine and magnesium including a decreased mean arterial pressure, systemic vascular resistance and increase in cardiac index.⁷ The magnesium dosing in the study was 5 grams over 20min followed by 3g/hr which is a higher maintenance dose than any of the campuses uses for neuroprotection.

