One of the largest studies that examined maternal and neonatal outcomes in the setting of preeclampsia was the Magpie trial,⁸ which had about 30% concurrent use with nifedipine and magnesium with no adverse effects reported. While on magnesium, all 5 campuses have mechanisms in place to monitor closely for magnesium toxicity including serial neurologic exams and/or magnesium levels. If any early adverse signs are seen, magnesium will be discontinued and/or calcium gluconate administered to reverse any neuromuscular blockade. For this reason, concomitant use of magnesium with either nifedipine or indomethacin is left to the judgment of the providers at each institution.

After 48 hours from the first dose of antenatal corticosteroids, the tocolytic agent will be discontinued. Maintenance tocolysis for longer than 48 hours will not be used on study patients. The study time required from each subject is the duration of hospital admission during which she is enrolled in the study and the duration of the birth hospitalization for each infant. To clarify, secondary outcomes measured will include delay of delivery by 7 days and decreasing delivery before 37 weeks as outlined in section 1 on page 2. Section 3 specifically asks the time required by study participants. Gestational age at delivery is an endpoint we plan to collect and the end of the study participants' time in the study. Gestational age at delivery will be collected as data but analyzed in a dichotomous fashion i.e. prior to 37 weeks. End points for tocolytic treatment are arrest of preterm labor (cervical dilation) or completion of betamethasone administration (e.g. 48 hours from the first dose). The primary study outcome is extension of pregnancy by 48 hours after admission. The secondary outcome is gestational age at delivery. We will also evaluate pregnancy extension by 7 days after treatment initiation. It is likely that some patients are discharged still pregnant and return later in gestation for delivery. Although no actual study time between these two time points are required of the subject or during subsequent hospitalization(s), data would be collected at the time of delivery.

For the neonates, data will be collected through discharge. No neonatal follow up is required. There may be subjects who deliver at another hospital. If the patient gives permission, then we will obtain records from the appropriate hospital.

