Subject's privacy will be protected by using HIPPA guidelines by limiting access to data collection study personnel only. In addition, data will always be kept in a secured, locked location. Subject screening, enrollment and case report forms will be kept in a binder that will be locked in a room/drawer at all times. These case report forms will be uploaded to a secure online database run by a well-established company Tiatros. Tiatros uses online software to organize, analysis and allow communication among principal investigators in the study. Most importantly this is done securely and follows HIPPA regulations.

Summary

This comparative study of nifedipine versus indomethacin for acute preterm labor will be conducted at the 5 UC medical campuses (UC Irvine, UC Davis, UC San Diego, UC San Francisco, UC Los Angeles) using the Reliance Agreement. UCI is the reviewing IRB. UC Davis, UCSD, UCSF, UCLA are the relying IRBs. All tocolytic treatment will be given in the primary hospital at each campus. Medication is discontinued once there is arrest of preterm labor, 48 hours from first dose of betamethasone, or when delivery is deemed imminent or unavoidable, and depending on institution's policy at the time magnesium initiated for neuroprotection. No maintenance tocolytic medication will be given (i.e. longer than 48 hours) and none will be given as an outpatient.

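### The two fetal harms the plan links to indomethacin, ductal constriction and oligohydramnios, are not among its outcomes

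*Combined protocol and SAP*

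**What the plan says.** The combined protocol and SAP raises these harms in the Indomethacin Treatment paragraph of Methods. Of the cited trial's regimen it says: "This regimen was associated with increased incidence of fetal ductal constriction (13/97) and oligohydramnios (5/97", each count being higher than in that trial's other two groups. It then draws a consequence for the dose: "Therefore, we propose using a one time loading dose of 100mg orally followed by 50mg every 6 hours, which is a commonly prescribed dosing". The paragraph ends: "Using the lower end of the normally prescribed dosing range should have decrease fetal and maternal side effects".

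Item 2 of Outcomes gives the infant list: "Neonatal outcomes measured will be respiratory distress syndrome (RDS), interventricular hemorrhage (IVH), patent ductus arteriosus (PDA), necrotizing enterocolitis (NEC", followed by intubation, NICU days and neonatal mortality. The maternal items are side effects serious enough to stop or delay the drug, and need for a second tocolytic. The outcomes restated in Objective and Methods concern prolongation of pregnancy and gestational age at delivery. The only ultrasound described is transvaginal cervical sonography, used to define preterm labor. No assessment of the ductus or of amniotic fluid is described.

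Existing Knowledge states that the trial is meant to settle which of the two drugs should be used first.

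**The concern.** The plan uses two specific fetal harms to choose its dose and predicts that the dose will reduce them, but does not plan to record either. The listed items do not fill the gap. Patent ductus arteriosus is a ductus that stays open after birth, not one that narrows before it. The maternal item does not cover fetal or amniotic-fluid findings.

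The Objective section hypothesises that indomethacin will do better at 48 hours. If it does, the trial could recommend indomethacin as first choice with nothing to report, by arm, on these two harms. The cited trial cannot simply supply the missing figures: Previous Research criticises it for including twins, for enrolling from 20 weeks and for crossover between drugs.

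**Working it through.** **1. The plan's figures.** The cited rates are 13/97 = 13.4%, exact (Clopper-Pearson) 95% CI 7.3 to 21.8%, and 5/97 = 5.2%, CI 1.7 to 11.6%. The arm size of 225 (Statistical Analysis) also reproduces. With two-sided alpha 0.05, 80% power, 72% versus 83% and mean rate 0.775, n = [1.960 × √(2 × 0.775 × 0.225) + 0.842 × √(0.72 × 0.28 + 0.83 × 0.17)]² / 0.11² = 225.04, or 226 rounded up. Nothing in this point changes it.

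**2. Harms named against outcomes listed.**

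| Harm named in Methods | Nearest listed outcome | Does it capture the harm? |
|---|---|---|
| Fetal ductal constriction | Neonatal patent ductus arteriosus | No: a different condition, after birth |
| Oligohydramnios | None | No |

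**3. How precise partial data would be.** The plan describes no scans, so the number assessed is unknown. With zero events in n women, the upper limit of the exact 95% interval is 1 − 0.025^(1/n). The assessed shares below are assumptions.

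| Share of the indomethacin arm | n | Upper limit |
|---|---|---|
| 100% | 225 | 1.6% |
| 50% | 112 | 3.2% |
| 25% | 56 | 6.4% |
| 10% | 22 | 15.4% |

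The limit falls below 13.4% at n = 26 (13.2%; 26/225 = 12% of the arm) and below 5.15% at n = 70 (5.13%; 70/225 = 31%). All these limits hold only if the women assessed are representative of the arm.

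**4. What suspicion-driven scanning can do.** Assume a true rate of 5% in both arms. On indomethacin, 80% of affected and 20% of unaffected women are assessed; on nifedipine, 30% of all women are.
- Indomethacin: affected and assessed 0.05 × 0.8 = 4.0%; unaffected and assessed 0.95 × 0.2 = 19.0%. Detected rate: 4.0/23.0 = 17.4% of women assessed, 4.0% of women randomised.
- Nifedipine: 0.05 × 0.3 = 1.5% of women randomised; 1.5/30 = 5.0% of women assessed.

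Equal true rates appear unequal on both denominators.

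**5. Why each finding needs its own assessed field.** Assume 112 women are scanned, the ductus is examined in 56, and 10% of those have constriction: 5.6 expected events. A single field for any scan gives 5.6/112 = 5.0%; a ductus field gives 5.6/56 = 10%.

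**6. Side check on the dose wording.** The only indomethacin range given is: "The dosing ranged from 50 to 100mg loading dose followed by 25mg to 50mg orally every 4-6 hours". The study's 100 mg load and 50 mg maintenance dose are its maxima; only the 6-hour interval is at the low-exposure end. Totals over 48 hours, counting maintenance doses before hour 48:
- study: 100 + 7 × 50 = 450 mg
- range minimum (6-hourly): 50 + 7 × 25 = 225 mg
- range maximum (4-hourly): 100 + 11 × 50 = 650 mg
- position: (450 − 225)/(650 − 225) = 53%

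Counting a dose at hour 48, the position is (500 − 250)/(700 − 250) = 56%. Either way the total is about mid-range.

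**The case against.** The strongest objection is to the remedy. Findings from clinically triggered scans in an open-label trial can mislead, and step 4 shows how they could count unfairly against indomethacin. That stands. It limits what may be claimed from the data and is why the proportion assessed must be reported, but it does not make no data preferable. Scheduled assessment in both arms would reduce the bias, but it is a new procedure and is not costed here.

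Outcome choice is also partly discretionary. The stated objective is efficacy, and several infant outcomes are collected through discharge. A reader might infer that the trial has no infant safety data; the documents do not support that. The case report forms are not reproduced, so relevant fields may exist on them, but no planned outcome uses them.

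A reader might also project the cited rates onto this trial (225 × 13/97 ≈ 30 constrictions, 225 × 5/97 ≈ 12 cases of oligohydramnios). The documents do not support this either: the cited trial included twins, enrolled at 20 to 32 weeks and gave the load rectally.

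On dose, the lower-end phrase may have been meant relative to the cited regimen: "initial 100mg suppository, repeated one time if contractions persisted after two hours, followed by 50mg orally every 6 hours". The stated changes in dose and route are no repeat load and an oral load. It is tempting to call these the only differences, but the cited regimen's duration is not given, while this plan stops treatment early: "Medication is discontinued once there is arrest of preterm labor, 48 hours from first dose of betamethasone". Under the literal wording, the plan's own range still does not support the phrase.

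**Conclusion.** The omission is clear from the text: two fetal harms are named and used to justify the dose, and neither is an outcome. As planned, the by-arm information on them is none. This is worth considering as a cheap improvement; it is not a flaw in the primary comparison, the sample size or the dose.

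Confidence is high for the omission and lower for how informative the added data would be, because the extent and pattern of scanning are unknown. The assessed shares in step 3 and all inputs to steps 4 and 5 are assumptions. By-arm data would describe detected harm by drug. They would not show that this dose is safer than another indomethacin dose, since no second dose is studied. The lower-end description is a wording matter and changes no result.

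**What to change.** 1. Add fetal ductal constriction and oligohydramnios to Outcomes, item 2, as descriptive safety outcomes from clinically obtained ultrasound.
2. For each finding record four items: assessed before treatment (yes/no) and result; assessed from treatment start to a fixed limit (yes/no) and result. The limit could be 7 days after the last dose, or delivery if earlier. State one definition of each finding for all five sites.
3. Report new findings by arm with exact 95% CIs, over women assessed and over women randomised, together with the proportion assessed in each arm. Make no formal comparison.
4. State as a limitation that ascertainment may be sparse, unequal or driven by suspicion, and that the data neither establish safety nor test the dose rationale.
5. Wording only: describe the dose as a single oral load with no repeat and a 6-hour interval, instead of placing it at the lower end of the range.

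**Cost:** 4 items × 2 findings = 8 fields per woman, or 8 × 450 = 3,600 entries, plus agreement on two definitions and one reworded sentence. No new procedure is needed. The main downside is that readers may over-interpret biased or sparse findings; items 3 and 4 make this visible but do not remove it.

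### The primary chi-square is valid but is not tied to any baseline covariate, and gestational age at delivery is analysed only as before 37 weeks; modest efficiency may be lost that is cheap to recover

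*Combined protocol and SAP*

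**What the plan says.** For the primary outcome, the Statistical Analysis section says: "The primary outcomes and other dichotomous outcomes will be evaluated using Chi-square". The only mention of modelling is "Regression analyses will be applied where appropriate such as for neonatal complications and the consideration of gestational age". That sentence does not name the primary outcome and fixes no covariates. Sites are to be compared in subgroup analyses.

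The Methods describe computer-generated block randomisation at five hospitals and do not say whether the blocks are stratified. Entry is before 32 weeks, and the definition of preterm labor uses, among other criteria, "cervical dilatation of > 2 cm at presentation or a change in cervical dilatation of > 1 cm". A short cervical length can also contribute to eligibility.

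On gestational age at delivery, the Methods say "Gestational age at delivery is an endpoint we plan to collect", then "Gestational age at delivery will be collected as data but analyzed in a dichotomous fashion i.e. prior to 37 weeks", and later "The secondary outcome is gestational age at delivery". The Objective and Outcomes sections list the rate of delivery before 37 weeks as a secondary outcome. The Statistical Analysis section also provides that "Continuous variables will be compared using Student's t-test".

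**The concern.** The sample size meets 80% power almost exactly, and no allowance for loss is stated, so there is no slack. Entry gestational age is known for every woman and cervical dilatation is assessed for most or all. If either predicts delivery within 48 hours, an adjusted analysis gives a tighter estimate from the same 450 women. Leaving regression to be used where appropriate also leaves the covariates to be chosen later, which is undesirable in an open-label trial.

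Gestational age at delivery is recorded for its own sake and then reduced to one yes/no split. A woman who gains four weeks but still delivers at 33 weeks counts the same as one who delivers on day 1. The plan's own t-test could be applied to the recorded value, so little new method is needed.

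**Working it through.** **1. The plan's own figure.** Inputs from the Statistical Analysis section: 72% and 83%, 80% power, alpha 0.05 (taken as two-sided, which reproduces the figure). With mean proportion 0.775:

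n per group = [1.960 × √(2 × 0.775 × 0.225) + 0.842 × √(0.72 × 0.28 + 0.83 × 0.17)]² / 0.11²
= [1.1575 + 0.4927]² / 0.0121 = 225.04.

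Power at 225 per group is 79.99%, so the stated size reproduces. In simulation the chi-square had type I error of 4.9-5.3%, so it is valid.

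**2. Primary outcome, adjusted.** The documents give no prognostic strength, so it is assumed over a range. Each setting used 6,000 simulated trials with 225 per arm, five sites, and marginal success of 72% versus 83%. The model had arm, site, entry age and dilatation. The unadjusted 95% CI half-width is 1.96 × √[(0.2016 + 0.1411)/225] = 7.65 points; the adjusted half-width is 7.65 × √(variance ratio).

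| Log-odds per SD, dilatation / entry age | Chi-square power | Adjusted power | Variance ratio | Half-width (points) |
|---|---|---|---|---|
| 0 / 0 | 80.0% | 79.4% | 1.019 | 7.72 |
| 0.4 / 0.2 | 81.1% | 82.3% | 0.980 | 7.57 |
| 0.8 / 0.4 | 80.6% | 85.2% | 0.907 | 7.28 |
| 1.2 / 0.4 | 79.6% | 86.7% | 0.822 | 6.93 |

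If dilatation does not predict and entry age has log-odds 0.2, 0.4 or 0.8 per SD, the ratios are 1.001, 0.982 and 0.919. A repeat at 0.4 gave 1.00.

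The approximation n/(1 - R²) agrees. R² = 0.02 gives 225/0.98 = 229.6 effective women per arm and 80.8% power; R² = 0.20 gives 225/0.80 = 281 and 88.0%. The adjusted analysis kept its error rate: type I error 5.0-5.4% (arm term) and 5.2-5.5% (standardised risk difference), with CI coverage of 94.0-94.8%.

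**3. Gestational age at delivery.** All inputs except 72% and 83% are assumed: entry age uniform from 24 to 32 weeks (no lower limit is stated as an entry criterion), later latency gamma with mean 4 to 8 weeks, delivery capped at 41 weeks.

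*Early-only difference* (28% versus 17% deliver within 48 hours, same course afterwards). Before the cap, the expected difference is about 0.11 × 4 = 0.44 to 0.11 × 8 = 0.88 weeks; with the cap it is 0.4-0.8. Across repeated simulations, power was:
- before 37 weeks, chi-square: 6-17%
- recorded age, t-test: 20-42%
- recorded age, adjusted for entry age: 27-47%

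Adjusting the binary outcome for entry age gave 7-18%, in effect no gain, so under this scenario the loss comes mostly from the cut. The CI half-width is 0.68-0.95 weeks unadjusted and 0.54-0.88 adjusted.

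*Early and late difference together* (a second model with Weibull latency): 66% with the cut, 81% with the t-test, 88% adjusted.

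*Late-only difference* (48-hour failure 22.5% in both arms, later latency 30% longer in one). T-test versus chi-square in six settings: 40 v 44, 63 v 65, 39 v 44, 59 v 68, 33 v 38 and 51 v 61%. The t-test is about 2 to 11 points lower. The adjusted model ranged from about 5 points lower to 13 higher.

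*The extra 11% all deliver between 48 hours and day 7*: every method has about 5% power, so there is no gain.

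**The case against.** The strongest reply is that nothing here is wrong. The test is valid, the size is right, and preferring an adjusted model is partly taste. The primary gain is small at plausible strengths and rests on assumed inputs. Dilatation may not be recorded for every woman, and with entry age alone the gain can be nil. All of this stands, and it limits the point to a cheap improvement.

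A second reply is that delivery before 37 weeks is a deliberate clinical target, listed in the Objective and Outcomes sections, and a mean difference in weeks answers a different question. That also stands. The binary outcome should stay, and the analysis in weeks should be added beside it. A reader might infer from "The secondary outcome is gestational age at delivery" that the plan is bound to analyse weeks, but the same section says explicitly that the analysis is dichotomous.

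A third reply is that the plan already allows regression. It does, but without covariates and without naming the primary outcome, so it commits to nothing there.

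A reader might also infer that randomisation is unstratified and that site can therefore be ignored. The Methods are silent on this. If blocks are within site, site belongs in the model.

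**Conclusion.** The point holds as a possible loss of efficiency. It does not support the stronger readings that the chi-square is biased, that 225 per group is wrong, or that recorded gestational age is always the more powerful analysis.

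For the primary outcome, adjustment is worth about 0 to 8 power points. The worst case costs about 2% in variance, when the covariates do not predict.

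For gestational age, removing the cut helps clearly if the treatments differ early, alone or together with a later difference. An early difference is plausible because tocolysis stops at about 48 hours. The gain is unreliable if the difference is only late, and absent if the extra women all deliver by day 7. Under the early-only scenario power stays below 50% by any method, so the benefit is an estimate in weeks with a narrower interval, not a powered test.

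The simulations treat 48-hour failure as delivery. The Methods also count the start of magnesium, after which some women do not deliver, so the true difference in weeks could be smaller. Prognostic strength, later latency and the lower entry age are all assumptions.

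**What to change.** Make these changes before outcome data are examined:

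1. **Primary outcome.** Specify a logistic model with arm, site and entry gestational age. Add entry cervical dilatation if it is recorded for every woman, including those whose eligibility rests on a short cervix. Report a standardised risk difference with 95% CI, which keeps the marginal comparison that the chi-square addresses. Keep the chi-square as a sensitivity analysis. State whether the randomisation blocks are within site.
2. **Gestational age at delivery.** Add an analysis of the recorded value in a linear model with arm and entry gestational age, reporting the difference in weeks with 95% CI. Keep delivery before 37 weeks as the stated binary secondary outcome.

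The cost is SAP wording and a little more analysis, with no extra patients. One baseline field may be needed if the case report form, which is not in the documents, does not already hold dilatation. The downside is that a model-based estimate is less simple to present than a 2×2 table and gains nothing if the covariates do not predict outcome.
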